### Hypotheses:

We hypothesize that with greater discount levels, there will be progressive increases in purchasing and intake of F&V and non-caloric beverages during the intervention period as well as improvement in health outcomes, which will be partially sustained during the follow-up period.

We predict greater relative increases in purchasing and consumption of F&V and improved health outcomes, among those with lower incomes as compared to those with higher incomes. F&V prices are relatively high compared with other foods, and are less affordable to those of lower income, who would be expected to benefit more from price reductions.

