### Specific Aims:

For the aims below, the first outcome (underlined) within each aim is primary, and the other outcomes are secondary.

**Primary Aim 1:** To investigate the effects of multi-level discounts on behavioral and health outcomes during the intervention period and their sustained effect during the follow-up period.

For greater price discounts ( $30\% > 15\% > 0\%$  group), we predict:

- a. *Purchasing Behaviors*
  - i. higher individual gross purchasing (i.e., price before discount) of F&V and non-caloric beverages
  - ii. reduced individual gross purchasing of less healthy, high energy dense (ED) highly processed foods (e.g., processed bakery items)
- b. *Consumption Behaviors*
  - i. higher individual F&V intake (g), the primary outcome measure (used to power the study), as assessed by 24-h dietary recalls and Brief Block Food Frequency Questionnaires (FFQ) (confirmed by biomarkers: plasma carotenoids and Vitamin C), as well as greater intake of non-caloric beverages
  - ii. decreased high energy-dense (ED) food intake (g), lower total fat intake (g), and lower daily energy intake (kcal)
- c. *Health Outcomes*
  - i. lower body weight (kg) and BMI ( $\text{kg}/\text{m}^2$ ), lower % body fat
  - ii. improved metabolic syndrome risk factors (fasting glucose, blood lipids, blood pressure)

	Protocol Name:	Multi-level supermarket discounts of fruits and vegetables on intake and health
	Principal Investigator:	[name]
	Primary Contact Name/Contact Info:	[name] [contact] [name] [contact]
	Date Revised:	8/7/20
	Study Number:	HS#: 16-00407 GCO#: 16-1050

**Primary Aim 2:** To investigate the effects of income as a moderator of outcome measures.

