### e) Endpoints

The primary endpoints will be at 40 and 56 weeks of participation. Once participants have started the intervention, data on compliance to the protocol will be collected at each visit by research staff and reviewed quarterly by the PI, the study statistician, and the safety officer. Compliance by participants will be evaluated by reviewing records. Data from subjects who show little or no purchasing during the first 8 weeks will be withdrawn from the study and from the analyses. If any serious issue arises, the study team will contact the individual to try to resolve any problems that exist. If the safety officer has concerns about whether compliance has reached a level that might inhibit the ability of the study to test its primary hypotheses, suggestions will be made for improving compliance.

An annual report will include a list and summary of adverse events. In addition, the annual report will address: (1) whether adverse event rates are consistent with pre-study assumptions, (2) reason for dropouts from the study, (3) whether all participants met entry criteria, (4) whether continuation of the

	Protocol Name:	Multi-level supermarket discounts of fruits and vegetables on intake and health
	Principal Investigator:	[name]
	Primary Contact Name/Contact Info:	[name] [contact] [name] [contact]
	Date Revised:	8/7/20
	Study Number:	HS#: 16-00407 GCO#: 16-1050

study is justified in order to collect additional data to accomplish the aims of the study, and (5) whether conditions are such that the study should be terminated prematurely. The annual report will be signed by the Safety Officer and will be forwarded to the IRB and to the NIH. A statement reflecting the results of the review will be sent to the NIH in the annual report (non-competing continuation). The adverse event form will be used by the study staff to report adverse events as they happen. The study statistician, the principal investigator, and the safety officer will review adverse event rates quarterly. Serious adverse events will be reported to the IRB, and if appropriate to NIH.

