step process. Subjects are guided through the previous 24-h to obtain food and beverage intake in five passes: pass 1 includes a quick list of foods and beverages consumed the previous day; pass 2 includes probe questions for foods forgotten during the quick list; pass 3 sorts foods chronologically and into eating occasions; pass 4 collects more details about the amount, preparation, and additions to the foods consumed; and pass 5 is a final review and probe for anything missed. The five-pass method provides multiple opportunities for subjects to remember and report additional foods and beverages. Special instructions and follow-up questions are incorporated. Subjects will be provided with food and beverage images via NDSR booklet materials to reduce error in estimating amounts. After all foods are coded and assigned weights, they will be reviewed, edited, and analyzed using NDSR which encompasses the USDA Food and Nutrient Database for Dietary Studies (FNDDS) and will provide weighted means for ED, calories, and macro- and micro-nutrient composition. (Duration: 15 min per phone recall)

**Dietary Measures:** The NDSR contains the great majority of supermarket food items and will provide an estimate of 24-h daily energy intake. For solid foods, we will calculate (g and serving sizes) high ED foods (> 4 kcal/g) and low ED foods (<1 kcal/g), mean energy density, as well as the daily fat content (g), a proxy for high calorie content. We will analyze F&V intake (g), which is the primary outcome measure (used to power the study). From the consumption of high ED foods, we will assess whether increased F&V intake displaces intake of high ED foods. Plasma carotenoids and Vitamin C will be used to corroborate the more subjective measure of 24-h dietary recall. In addition, the Brief Block Food Frequency Questionnaire (FFQ) will be administered to corroborate the dietary assessments.

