Multi-level Supermarket Discounts of Fruits and Vegetables' Impact on Intake and Health
PI: [name]
NCT04178824
Document Date: 8-1-2023

Statistical Analysis Plan

Linear mixed effects modeling was performed to evaluate the group-by-time interaction of all outcomes from the intent-to-treat (ITT) sample, as a primary analysis, and the per-protocol sample, as a secondary analysis. The ITT sample was comprised of participants with at least one post-randomization measurement. The per-protocol sample was comprised of all participants who completed the study. Primary outcome measures were grams (g) of fruit, vegetable, non-caloric beverage intake, and body weight (expressed in kilograms (kg)). Secondary dietary outcomes were high-ED food intake (g), total fat intake (g), and daily energy intake (kcal). Secondary clinical outcomes were BMI (kg/m²), percent body fat, waist circumference (cm), metabolic risk factors (fasting glucose (mg/dL), cholesterol (mg/dL), and blood pressure (mmHg). The linear mixed model included the group-by-time interaction term, where time was the within-subjects factor and group was the between-subjects factor (fixed effects), and the participant as the random effect to obtain the within-person differences in response to the intervention. No covariates were added to the main model because there were no baseline differences in covariates between discount groups and the RCT study design reduces between-group differences (29). First, an omnibus test was performed to test the overall effect of the group-by-time on interaction on the outcome variables. Then, a planned comparison approach using difference-in-difference contrast (DiD) was done to evaluate the differential change in primary outcome variables. The main comparison of interest was the change between groups between the baseline and the first 16 weeks of the intervention (the mid-point of the intervention period), 32 weeks of the intervention (the end of the intervention period), and 16 weeks post-intervention (the end of the follow-up period). A sensitivity analysis was also performed on the ITT sample by adding key covariates to the model: sex, age at enrollment, season at enrollment, primary supermarket, COVID presence, and income level. The presence of COVID was assigned if the COVID-19 pandemic and lockdown period occurred during the intervention between 2/20/20 and 4/6/2021. The absence of COVID-19 was assigned if the COVID-19 pandemic period happened prior to or after the intervention. Income level was a dichotomous variable: above or below the median income in NYC. Estimated means and 95% confidence intervals are shown in tables and figures. Missing data was assumed to be missing at random (MAR). Two-tailed $P < .05$ was considered statistically significant. RStudio (RStudio version 2023.12.0 Build 369) was used to analyze all data.

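### The SAP tests three or four primary outcomes at three times at P<.05 with no deciding test or multiplicity control, and does not clearly list the summed F&V intake that powered the study

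*SAP*

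**What the plan says.** The protocol singles out one outcome twice. Specific Aims, Aim 1 b.i, has "higher individual F&V intake (g), the primary outcome measure (used to power the study", and Measures (Dietary Measures) has "We will analyze F&V intake (g), which is the primary outcome measure (used to power the study". Section 5e sets the times: "The primary endpoints will be at 40 and 56 weeks of participation".

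Specific Aims also gives a general rule, that "the first outcome (underlined) within each aim is primary" and the others are secondary. Under Aim 1, item a.i is gross purchasing. Item b.i goes on to say "as well as greater intake of non-caloric beverages", and item c.i opens with "lower body weight (kg) and BMI". The Hypotheses expect that "with greater discount levels, there will be progressive increases in purchasing and intake of F&V and non-caloric beverages", and Aim 1 orders the groups 30% > 15% > 0%.

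The SAP states: "Primary outcome measures were grams (g) of fruit, vegetable, non-caloric beverage intake, and body weight". It describes an omnibus group-by-time test, followed by difference-in-difference (DiD) contrasts on the primary outcomes. The changes of main interest run from baseline to 16 weeks of intervention, 32 weeks of intervention and 16 weeks after it. The only threshold is two-tailed P<.05.

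The SAP does not say whether a null omnibus test stops the contrasts, which group pairs count, which result decides the trial, or how error is controlled across outcomes and times.

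**The concern.** As written, a P value below .05 on any listed outcome, at any of three times, could be presented as the trial's primary finding. A significant beverage contrast at week 24 would qualify, although section 5e does not name that time. Meanwhile the outcome that powered the study has no clearly stated test of its own. The issue is what the trial may conclude, because the error rate attached to a primary claim is not 5% and cannot be read off the plan.

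**Working it through.** **No plan figure to reproduce.** The documents give no family-wise error rate, and no power, effect size or SD for F&V intake.

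**Inputs from the documents.** Two-sided .05 per test, three post-baseline times, and the primary list (SAP). Three groups (Study Visit 2). 360 × (1 − 0.375) = 225 completers (section 5c), so 225 / 3 = 75 per arm with equal arms.

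**Assumptions.** No true effect on any listed outcome; a common outcome correlation of 0 to 0.8; four times (baseline and weeks 24, 40, 56); a random-intercept model with compound symmetry. Arm size and within-person correlation barely matter, because DiD contrasts cancel the person effect.

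**Times.** The intervention starts at week 8, so the SAP's times are 8 + 16 = week 24, 8 + 32 = week 40 and 40 + 16 = week 56. Week 24 is the addition to section 5e.

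**Counts.** The omnibus test has (3 − 1) × (4 − 1) = 6 df. With four outcomes there are 4 × 3 times × 3 pairs = 36 contrasts, or 24 against 0%, or 12 for 30% vs 0%. With fruit and vegetable as one outcome these are 27, 18 and 9.

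**Independent case.** One omnibus test per outcome gives 1 − 0.95⁴ = 18.5% for four outcomes and 1 − 0.95³ = 14.3% for three.

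**Simulation** (200,000 to 400,000 null trials per setting). Chance of at least one false-positive primary result, as correlation goes from 0 to 0.8:

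| What counts as a positive | Four outcomes | Three outcomes |
|---|---|---|
| Any omnibus test | 18.4% → 12.2% | 14.4% → 10.4% |
| Omnibus gates, any pair | 17.3% → 11.6% | 13.6% → 9.8% |
| Omnibus gates, either discount vs 0% | 15.7% → 10.6% | 12.2% → 8.9% |
| Omnibus gates, 30% vs 0% only | 10.5% → 7.3% | 8.1% → 6.0% |
| No gate, any pair | 73.6% → 53.2% | 63.4% → 47.9% |
| No gate, either discount vs 0% | 62.6% → 43.7% | 52.5% → 38.8% |
| No gate, 30% vs 0% only | 41.5% → 26.8% | 33.2% → 23.4% |

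A separate large-sample simulation of all but the two 30%-vs-0%-only rows agreed to within a few tenths of a percentage point. With AR(1) time correlation of 0.5 in place of compound symmetry, the gated discount-vs-0% figure at outcome correlation 0.8 is 9.9% (four outcomes) or 8.4% (three). At outcome correlation 0.9 with four outcomes, the gated rows run from 9.7% down to 6.0%.

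**Summed F&V intake alone at weeks 40 and 56.**
- Three pairs × two times = six contrasts: 21.4% unadjusted, 4.3% with Holm.
- Two discount-vs-0% pairs × two times = four contrasts: 16.2% unadjusted, 4.4% with Holm.

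So naming the outcome without controlling the contrasts is not enough.

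**Power cost.** A contrast with 80% power at .05 has a standardised shift of 1.960 + 0.842 = 2.802. At Holm's first step with m contrasts, power is Φ(2.802 − z), where z is the two-sided critical value at .05/m:
- m = 4 (.0125): Φ(2.802 − 2.498) = 62%
- m = 6 (.0083): Φ(2.802 − 2.638) = 56%
- m = 8 (.00625): Φ(2.802 − 2.734) = 53%
- m = 12 (.0042): Φ(2.802 − 2.865) = 47%

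**The case against.** **The omnibus test may protect the contrasts.** The SAP's order of testing suggests a gate. If there is one, it limits error within an outcome but not across three or four outcomes. The lowest gated reading (30% vs 0% only) gives about 6–10%, which is a modest excess. That stands, and the larger figures should not be quoted without it. The 74% figure needs all 36 contrasts to count, uncorrelated outcomes and no gate. The SAP does not rule this out, but nothing shows it was intended.

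**Fruit and vegetable may be one outcome.** The SAP's comma list allows it. A reader might infer that the powered outcome was split or dropped, but the wording does not establish that. The multiplicity problem remains with three outcomes.

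**Body weight and beverages may be protocol primaries.** A reader might infer that the SAP promoted them. The documents do not support that: the protocol marks primaries by underlining, which the text read here does not show. By the same rule purchasing (a.i) could be primary, since it is listed first under Aim 1.

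**The protocol does not dictate the contrasts.** This is correct. It gives the outcome, the times and the 30% > 15% > 0% ordering. Comparing only each discount with 0% would be an analyst's choice.

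**The measurement source is not settled either.** Aim 1 b.i names both 24-h recalls and the food frequency questionnaire (FFQ), while Dietary Measures treats the FFQ as corroborating. Recall timing is given three ways: between visits (Study Visit 1), in the weeks after visits (Study Visit 2-5) and mid-period (24-h Dietary Recalls). This is a matter of endpoint definition rather than multiplicity, but a deciding test cannot be written until it is resolved.

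**Conclusion.** The point holds and should be fixed before any result is called primary. The week-24 comparison is a clear addition to the protocol's endpoints. Summed F&V intake is not clearly listed in the SAP, and whether it was split is a question for the sponsor.

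On every reading examined, the chance of at least one false-positive primary result exceeds 5%: about 10–19% (9–14% with three outcomes) if omnibus tests decide or gate all-pairs or discount-vs-0% contrasts; about 7–10% (6–8%) if gated with only 30% vs 0% counting; about 27–74% (23–63%) with no gate. These figures assume no true effect on any listed outcome and a correlation of 0 to 0.8, which the documents do not give. They are not the probability that a particular significant result is false.

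A reader might also infer that the primary list was chosen after seeing results. The SAP is in the past tense and already reports baseline comparisons, so it cannot be shown to predate the data. That does not show that results drove the choice.

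**What to change.** In the SAP:

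1. Make summed F&V intake (fruit g + vegetable g) at weeks 40 and 56 the deciding outcome. Say whether fruit and vegetable were analysed as a sum, and call it a departure from the protocol only if they were split. State whether recalls or FFQ decide (recalls fit Dietary Measures), and which recall set stands for each endpoint.
2. Control two-sided 5% error by Holm or a stated fixed sequence. Six contrasts (three pairs at two times) lie closest to the protocol's predicted ordering. If only the four discount-vs-0% contrasts are used, say that this is an analyst's choice and not taken from the protocol.
3. State whether the omnibus test gates the contrasts.
4. Check the formatted protocol page. If purchasing, beverage intake or body weight is underlined as primary, add its contrasts to the same family; otherwise report it as secondary.
5. Report week 24, fruit alone and vegetables alone as secondary, and label week 24 as an addition to the protocol's endpoints.
6. State that the outcome and times are taken from the protocol because the SAP cannot be shown to predate the data.

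This costs SAP wording, one summed variable and relabelled results. Some nominally significant results become secondary. An assumed 80% power at .05 drops to the first-step values worked out above, and each outcome added under item 4 lowers it further. A fixed sequence keeps the full .05 for its first contrast but stops at the first failure.

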### **Brief Summary of Research (250-400 words):**

Our objective is to test the effect of various supermarket discount levels on fruit and vegetable (F&V) and non-caloric beverage purchasing and consumption, as well as health outcomes. We will implement this economic intervention in a local supermarket chain to assess the effects of a 32-week intervention of fruit and vegetable (F&V) and non-caloric beverage discounts of 30%, 15%, and 0% (control group) on purchasing, dietary intake, and health outcomes, including body weight and composition, blood pressure, and biochemical markers of cardiovascular disease risk. The 32-week intervention will be preceded by an 8-week baseline and will have a follow-up period of 16 weeks. There will be no discounts in effect during the baseline and follow-up periods.

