**Income questionnaire (Appendix B)** will be used to obtain additional income information. This questionnaire will be emailed only prior to visit 1. (Duration: 5 min)

**Behavioral Checklist:** A brief structured interview will help ensure adherence, e.g., no change in smoking, diet, medications, etc. Deviations will be controlled for if imbalanced by group. This questionnaire will be completed at or close to the screening visit and during subsequent study visits. (Duration: 10 min)

**Appetite Ratings:** Visual Analogue Scales (VAS) will be used to rate hunger and satiety (**Appendix E**) on the 5 morning visits. Questions include “How hungry do you feel?”, “How full do you feel?”, and “How much is your desire to eat?” with anchors for “Extremely” and “Not at all” to help assess whether increases in F&V intake alters appetite. (Duration: 1 min)

**Fruit, Vegetable, and Snack Food Liking (Appendix F):** This measure contains ratings of 5 frequently eaten items from the categories of fruits, vegetables, and snack foods. Food preferences may change after exposure and eating behavior of F&V [160], with increases in F&V liking, which may help sustain the intervention effects. It has been shown that preference increases for previously disliked vegetables after 9-10 taste exposures [161]. Although the majority of this research has been in children, it may also occur in adults [162]. (Duration: 4 min)

**Brief Block Food Frequency Questionnaire (FFQ):** will be administered to corroborate the 24h-dietary recalls and purchasing data. (Duration: 15 minutes)

**Physical Assessments:** All anthropometric measures will be made in duplicate at wk 0, 8, 24, 40, 56 on S&R 11 in the patient examining room by trained research technicians blind to the subjects' group assignment. Subjects will be asked to use the bathroom to void and to remove footwear and empty pockets prior to measurement.

1. Height will be measured with a stadiometer (at Screening Visit only)

	Protocol Name:	Multi-level supermarket discounts of fruits and vegetables on intake and health
	Principal Investigator:	[name]
	Primary Contact Name/Contact Info:	[name] [contact] [name] [contact]
	Date Revised:	8/7/20
	Study Number:	HS#: 16-00407 GCO#: 16-1050

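### The main model's difference-in-difference contrasts give up precision on intake by not adjusting for baseline, and the covariance behind the weight contrasts is not stated

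*SAP*

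**What the plan says.** The SAP describes a linear mixed model with group, time and group-by-time as fixed effects "and the participant as the random effect to obtain the within-person differences in response to the intervention". After an omnibus test, "a planned comparison approach using difference-in-difference contrast (DiD) was done to evaluate the differential change in primary outcome variables", comparing baseline with three later points: mid-intervention, end of intervention and end of follow-up (study weeks 24, 40 and 56). On adjustment it says "No covariates were added to the main model because there were no baseline differences in covariates between discount groups". The sensitivity model adds sex, age, season, supermarket, COVID period and income, but not the baseline value of the outcome. On reporting: "Estimated means and 95% confidence intervals are shown in tables and figures". No residual covariance, visit-specific variance or robust standard error is named. The SAP does not say that the baseline means are constrained to be equal. Group as a fixed factor, with a contrast that subtracts each arm's own baseline, implies that they are free.

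The Protocol (Measures, Dietary Measures) says "We will analyze F&V intake (g), which is the primary outcome measure (used to power the study". The recalls behind that outcome are taken mid-period, between visits (Measures, 24-h Dietary Recalls; Study Visit 1). The SAP lists intake and body weight as primary outcomes. For weight, "All anthropometric measures will be made in duplicate at wk 0, 8, 24, 40, 56" (Physical Assessments). Weeks 0 and 8 both precede the discounts, and the SAP does not say which is the weight baseline.

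**The concern.** The SAP justifies an unadjusted model by the absence of baseline differences between groups. That answers a worry about bias. It does not address precision, which is the main reason to adjust for the baseline outcome in a randomised trial. The baseline values are already collected, so the loss is avoidable. It falls mainly on intake, where a few recalls per period make a correlation well below 1 plausible.

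The second issue is narrower. A single participant random effect, read in the usual way, gives every change contrast the same standard error. The design gives reason to doubt that this suits weight. The Protocol says "There will be no discounts in effect during the baseline and follow-up periods" (Brief Summary of Research) and expects effects "which will be partially sustained during the follow-up period" (Hypotheses). The spread of weight change could therefore keep growing to week 56, or peak at week 40 and fall back. Weeks 40 and 56 are the Protocol's endpoints (section 5e). Until the covariance is stated, a reader cannot judge which weight intervals to rely on.

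**Working it through.** **The plan's own figure.** Protocol section 5c: 360 x (1 - 0.375) = 225 completers, which reproduces; that is 75 per arm if allocation is equal (the ratio is not stated). The documents give no power, effect size, intake SD or intake correlation, so the loss cannot be tied to a planned power.

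**(a) Intake.** Assumptions: complete data, equal baseline and follow-up variances, correlation rho. Per unit of outcome variance:

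- DiD: 2(1 - rho)
- baseline-adjusted or common baseline mean: 1 - rho^2
- ratio, adjusted to DiD: (1 + rho)/2

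| rho (assumed) | DiD | Adjusted | Ratio | Interval narrower by | DiD n per arm to match 75 adjusted | DiD power where adjusted has 80% |
|---|---|---|---|---|---|---|
| 0.2 | 1.60 | 0.96 | 0.60 | 23% | 125 | 58% |
| 0.4 | 1.20 | 0.84 | 0.70 | 16% | 107 | 65% |
| 0.7 | 0.60 | 0.51 | 0.85 | 8% | 88 | 73% |

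The narrowing is 1 - sqrt(ratio), and the matching n is 75/ratio. A 4,000-replicate simulation at rho 0.3, 0.5 and 0.6 gave ratios of about 0.65, 0.75 and 0.80, as the formula predicts. Below rho 0.5, DiD is less precise than comparing follow-up means alone, because 2(1 - rho) exceeds 1. With unequal SDs s0 (baseline) and s1 (follow-up), the variance saved is (s0 - rho s1)^2, so in large samples with complete data adjustment does not lose.

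The planned sensitivity model does not recover this. In a complete-data fit, adding a time-invariant covariate as a main effect left the DiD estimates and standard errors unchanged (0.3202 with and without).

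For weight, take the preliminary study's SD of change of 1.8 kg (50% discount arm, 8 weeks) and an assumed between-person SD of 15 kg. Then rho = 1 - 1.8^2/(2 x 15^2) = 0.9928 and the ratio is 0.996. For SDs of 12 to 18 kg it is 0.994 to 0.998.

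**(b) Weight, only if a random intercept with independent, equal-variance residuals was fitted.** With complete data at weeks 8, 24, 40 and 56 (week-8 baseline), the fitted change variance is the same at every visit: the average of the six pairwise change variances. Type I error is 2[1 - Phi(1.96 x sqrt(fitted/true))].

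*Growing spread.* Let change variance at t weeks after week 8 be (1 - f)(1.8^2/8)t + f x 1.8^2, where f is the share that is visit-level noise.

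- f = 1 (constant): 5.0% at all three visits.
- f = 0.9: true 3.56, 4.21, 4.86; fitted 4.00; type I error 3.8%, 5.6%, 7.6%.
- f = 0: true 6.48, 12.96, 19.44; fitted 10.8; type I error 1.1%, 7.4%, 14.4%.

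*Response in the two discount arms only, peaking at week 40 with half left at week 56.* Assume residual SD 1 kg and response SD r of 1.5 to 3.5 kg. At week 40 the change variance is 2 + r^2 in a discount arm and 2 in the control arm. The fitted value, pooled over three arms, is 2 + (2/9)r^2.

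- Discount versus control, true 4 + r^2 against fitted 2 x [2 + (2/9)r^2]: 6.25 against 5.00 (8.0%) to 16.25 against 9.44 (13.5%).
- 30% versus 15%, true 4 + 2r^2 against the same fitted values: 8.5 against 5.00 (13.3%) to 28.5 against 9.44 (25.9%).
- With one unstructured covariance shared by all arms, the fitted value becomes 2 x [2 + (2/3)r^2], that is 7.0 to 20.3. Error is then about 3-4% for discount versus control and 7.5-10% for 30% versus 15%.

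**The case against.** DiD is a valid, planned estimator, and choosing another is partly a matter of preference. That stands as to validity. A reader might infer that the DiD results are biased, but under randomisation they are not; the loss is of precision only, and its size rests on a correlation that the documents do not give.

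A reader might also combine planned dropout with the visit weeks to get intake gains at weeks 24, 40 and 56. The documents do not support that, because intake recalls are taken between visits, so retention at visit weeks does not describe them. Only the complete-data range is quoted here.

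A common baseline mean has a cost. The ITT sample requires a measurement after randomisation, and participants learn their arm at week 8. If early loss differs by arm, the analysed arms need not share a baseline mean. DiD does not impose that equality. This objection stands and belongs with the fix.

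Finally, a reader might infer that the weight intervals are wrong. Nothing in the documents shows this: the covariance is unstated, constant change variance gives 5% at every visit, and (b) falls away if a flexible structure was used. The growth case also stretches an 8-week SD to 48 weeks; at f = 0 it implies a change SD of sqrt(19.44) = 4.4 kg. Those figures are illustrations.

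**Conclusion.** The efficiency point holds for intake. Adjusting for the baseline outcome would cut variance by 15-40% and narrow intervals by 8-23%, given complete data, equal variances and an assumed rho of 0.2 to 0.7. The planned sensitivity covariates do not recover it, and for weight there is almost nothing to gain.

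The covariance and the choice of week 0 or week 8 are reporting gaps, not demonstrated errors. If a random intercept with independent, equal-variance residuals was used, week-56 type I error would be about 8-14% under the illustrative growing spread. Week-40 error would be about 8-14% (discount versus control) or 13-26% (30% versus 15%) under the illustrative peaked response. These are reasons to use a flexible covariance in the added model. They do not by themselves discredit the weight results.

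**What to change.** Keep the DiD results. State the covariance structure used in that fit and whether the weight baseline is week 0 or week 8. Beside them, report a model with the baseline outcome as a covariate by time (or a common baseline mean) and an unstructured within-person covariance, with 95% intervals for the three planned contrasts. The SAP reports a completed analysis, so label this model as added afterwards. If a contrast crosses P < .05 in only one model, show both and do not replace the DiD result. For weight, if spread differs by arm, one shared unstructured covariance is only a partial remedy; an arm-specific covariance or robust standard errors would be needed.

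Cost: no new data. With four visits, the unstructured covariance has 10 parameters against 2 for a random intercept, and a common baseline mean removes 2 mean parameters. If the common mean is used, report baseline means and early loss by arm so that readers can judge the constraint. Some weight intervals may widen. Relative to a random-intercept fit, the f = 0 case widens week 56 by sqrt(19.44/10.8) - 1 = 34% and narrows week 24 by 1 - sqrt(6.48/10.8) = 23%.
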